### **Analysis:**

Analyses conducted based on the FAS will be based on the assigned randomized treatments.

The safety analysis set will be defined as all randomized subjects who have received at least 1 dose of study medication and subjects will be analyzed according to the actual study treatments they receive.

Unless specified otherwise, all data will be summarized by treatment group. Continuous variables will be presented using descriptive statistics. Categorical variables will be summarized using subject counts and percentage of subjects in corresponding categories.

The primary efficacy evaluation is the change from baseline of OHSA#1 at Week 4. Baseline is defined as Day 1 pre-dose measurement. Mixed model for repeated measures (MMRM) will be used to compare treatment differences. The model will include fixed effect class terms of treatment, baseline disease type (MSA, PD, PAF), week, and continuous covariate of baseline OHSA#1 score, a random subject effect, with an unstructured covariance structure using the FAS.

Least-square means and 95% confidence intervals on the differences between TD-9855 and placebo will be calculated and presented.

Missing data in the MMRM analysis is assumed as missing at random (MAR) and will not be imputed for the analysis of the primary endpoint. Sensitivity analyses on the primary endpoint will be conducted using multiple imputation. The primary analysis will be repeated on a set of pre-specified subgroups and presented in graphical format.

If the treatment effect of the primary efficacy endpoint has been demonstrated, the following secondary efficacy endpoints will be tested via statistical testing procedure, to be described in the statistical analysis plan (SAP), that will protect the family-wise Type I error rate at 2-sided significance level of 5% until a failure to reject the null hypothesis occurs. No statistical significance will be claimed after a failure to reject the null hypothesis has occurred.

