6.1.3. Safety Analysis Set

The safety analysis set comprises all randomized subjects who receive at least 1 dose of study medication. The safety analysis set will be the analysis set for both general (baseline, exposure, and compliance) and safety analyses. Subjects in the safety analysis set will be grouped according to the study treatments they receive.

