The analysis of safety and tolerability data includes an overall summary of adverse events, drug exposure (duration of treatment), dosing information/compliance, concomitant medications, clinical laboratory results, vital signs, ECGs, and C-SSRS.

In general, inferential statistical tests are not performed for the analyses of safety and tolerability data.

For all safety analyses, the safety analysis set will be used. The listing of TEAE and vitals signs will be provided using the randomized analysis set to include the subjects from site 27045.

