9.1. Adverse Events

Adverse events are collected from signing of the informed consent through the end of follow-up. Adverse events will be coded to the preferred terms of the Medical Dictionary for Regulatory Activities (MedDRA®, version 24.0).

A treatment-emergent adverse event (TEAE) will be defined as any AE that begins on or after the date of first dose of study drug up to 14 days after the date of last dose of study drug. However, for patients who continued into Study 0170, any AE occurs after Study 0170 Visit 1 (Study 0169 Visit 6) will be considered as a TEAE for Study 0170 and will not be included in the AE summary for Study 0169 to avoid double counting.

AEs observed during the period from obtaining informed consent to the start of administration of study drug will not be considered as TEAEs and will be listed only.

AEs and TEAEs will be listed by subject. In addition, subjects with AEs leading to permanent or temporary discontinuation of treatment will be listed separately.

TEAEs will be summarized overall with counts and percentages of subjects with the events, by treatment group, system organ class, and preferred term. TEAEs leading to permanent or temporary discontinuation of treatment, related to study treatment (i.e., any reported as related), serious TEAEs, frequent TEAEs (defined as >3% in the study population), TEAEs by severity, TEAEs of special interest, deaths, and TEAEs by maximum severity and causality will be summarized.

If no adverse events meeting a specific table criterion are observed, the summary table will indicate that there were no occurrences.

9.1.1. [REDACTED]

[REDACTED]

[REDACTED]

[REDACTED]

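### Does the SAP's site-specific listing rule keep dosed subjects at site 27045 out of the safety tables?

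*SAP*

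**What the plan says.** SAP section 9 opens with a general rule: "For all safety analyses, the safety analysis set will be used". It then adds: "The listing of TEAE and vitals signs will be provided using the randomized analysis set to include the subjects from site 27045". The readable text mentions this site nowhere else.

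SAP 6.1.3 defines the set: "The safety analysis set comprises all randomized subjects who receive at least 1 dose of study medication". It also states its use: "The safety analysis set will be the analysis set for both general (baseline, exposure, and compliance) and safety analyses". The Analysis part of the protocol synopsis agrees: "The safety analysis set will be defined as all randomized subjects who have received at least 1 dose of study medication". Neither definition carries a site exception. SAP 6.1.2 defines the randomized set simply as everyone randomized.

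SAP 9.1 defines a TEAE as "any AE that begins on or after the date of first dose of study drug", within a limit after the last dose. Events between consent and the "start of administration of study drug will not be considered as TEAEs and will be listed only". On output, "AEs and TEAEs will be listed by subject".

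Two other places bear on the point. SAP 7.3, on protocol deviations, ends by basing subject listings in general on the randomized set. The disposition summary in SAP 7.2 reports the size of each analysis set and, separately, how many randomized subjects were and were not treated.

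**The concern.** A switch to a wider population for the sake of one site makes sense only if that site's subjects are missing from the narrower one. The narrower one here is the safety set, and its definition gives no ground for leaving out a dosed subject. Naming TEAEs makes this sharper: a TEAE needs a first dose, so a subject with one has been dosed and already belongs to the safety set. Taken at its word, the sentence hints at an exclusion that is written nowhere.

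If such an exclusion were applied to dosed subjects, their adverse events, serious events and deaths would appear in listings but not in the tables by treatment group. Their exposure, laboratory, ECG and C-SSRS data would also be absent from the summaries. That would contradict SAP 6.1.3 and the protocol.

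**Working it through.** The plan gives no figure to reproduce on this point. The check is mainly one of set definitions.

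**What the switch of population adds.** Let R be the randomized set (SAP 6.1.2) and S the safety set (SAP 6.1.3). R minus S is then the randomized subjects who never took a dose. By SAP 9.1 such a subject cannot have a TEAE, so moving the TEAE listing from S to R adds no TEAE rows. The vital signs listing can gain rows, because the schedule (SAP Table 2) takes vital signs at screening and at Visit 2, before the first dose on the following morning. That overnight gap also makes a randomized but undosed subject a realistic case, and SAP 7.2 has a line for it.

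**The possible readings.**

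- *Site subjects never dosed.* They are outside S by definition. The safety tables are unaffected, the vital signs listing gains their pre-dose values, and any events they had since consent are AEs to be listed. The only fault is that the sentence says TEAE where AE fits.
- *Site subjects dosed.* SAP 6.1.3 puts them in S and every safety summary counts them. The site clause is then redundant but harmless.
- *Dosing cannot be confirmed.* The first-dose condition is not shown to be met, and listing on R keeps the data visible. The readable text does not say whether this applies.
- *Site subjects dosed but deliberately excluded.* Only this reading does harm. No readable passage states it, and it contradicts SAP 6.1.3.

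**What the harmful reading would cost.** The number of subjects at the site, their dosing status and their events are not given, so the following only shows scale; the event counts are assumed. SAP 4.4 gives at least 76 subjects as at least 40% of enrolment. Rounding 0.40 × N up gives 76 for N = 188 (75.2), 189 (75.6) and 190 (76.0), but 75 for 187 (74.8) and 77 for 191 (76.4). Hence N is 188 to 190, or 94 to 95 per arm at 1:1.

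- One serious event, with its subject omitted: 1/95 = 1.05% becomes 0/94 = 0%.
- An event in 10 of 95 (10.53%): omitting one affected subject gives 9/94 = 9.57%, down 0.95 points; omitting one unaffected subject gives 10/94 = 10.64%, up 0.11 points.
- The frequent-TEAE table (more than 3% of the study population, SAP 9.1): 6/190 = 3.16% qualifies, while 5/189 = 2.65% does not.
- No subject dosed: change = 0.

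Even the direction of an effect on a rate depends on who would be omitted.

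**The case for a change.** The best case for acting is that SAP 6.1.3 is fully readable and has neither an exception nor a cross-reference that matches section 9. The TEAE half of the sentence is empty unless dosed subjects are outside the safety set. Listings are on the randomized set anyway under SAP 7.3, so a site-specific reason points to a special status that the definition does not record. The SAP calls itself the final authority on analyses: one programmer might follow 6.1.3, another the hint in section 9. Settling it would take a sentence or two.

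The mismatch in wording stands. The step from there to altered safety tables does not. A programmer builds the safety set from its definition, not from the purpose clause of a sentence about listings. SAP 7.3 sits in the protocol-deviation section, so its reach can be argued, but at face value it makes a randomized-set listing ordinary rather than a departure. SAP 9.1 already calls for AEs as well as TEAEs to be listed by subject, so loose use of the narrower term is an easy slip.

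The site's status may also be explained in text that is blacked out: protocol 8.3 (analysis sets), protocol 8.3.2 (major deviations) or SAP Appendix 1 (changes to protocol-planned analyses). A request to state it could ask for something the plan already contains.

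**Conclusion.** No change follows. This is an imprecise sentence about two listings, and analysts can apply it sensibly. Under the definitions as written, every randomized subject with at least one dose is counted in all safety summaries, site 27045 included, so the effect on those tables is zero. The full analysis set in SAP 6.1.4 names no site exclusion either, and the sentence does not touch the efficacy analyses.

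This rests on SAP 6.1.3 being applied literally and on no contrary rule standing in the redacted sections. Planned output would show a departure: in the SAP 7.2 disposition summary, the number randomized and treated must equal the size of the safety set. If the two differ, dosed subjects have been left out, and that would be an error of execution against SAP 6.1.3 rather than a defect in the plan.

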9.1. Adverse Events

Adverse events are collected from signing of the informed consent through the end of follow-up. Adverse events will be coded to the preferred terms of the Medical Dictionary for Regulatory Activities (MedDRA®, version 24.0).

A treatment-emergent adverse event (TEAE) will be defined as any AE that begins on or after the date of first dose of study drug up to 14 days after the date of last dose of study drug. However, for patients who continued into Study 0170, any AE occurs after Study 0170 Visit 1 (Study 0169 Visit 6) will be considered as a TEAE for Study 0170 and will not be included in the AE summary for Study 0169 to avoid double counting.

AEs observed during the period from obtaining informed consent to the start of administration of study drug will not be considered as TEAEs and will be listed only.

AEs and TEAEs will be listed by subject. In addition, subjects with AEs leading to permanent or temporary discontinuation of treatment will be listed separately.

TEAEs will be summarized overall with counts and percentages of subjects with the events, by treatment group, system organ class, and preferred term. TEAEs leading to permanent or temporary discontinuation of treatment, related to study treatment (i.e., any reported as related), serious TEAEs, frequent TEAEs (defined as >3% in the study population), TEAEs by severity, TEAEs of special interest, deaths, and TEAEs by maximum severity and causality will be summarized.

If no adverse events meeting a specific table criterion are observed, the summary table will indicate that there were no occurrences.

9.1.1. [REDACTED]

[REDACTED]

[REDACTED]

[REDACTED]

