Safety assessments will include a physical examination, neurological examination, vital signs (body temperature, HR and BP), body weight, ECGs, safety laboratory tests (hematology, chemistry, and urinalysis), C-SSRS, and AEs.

Safety will be periodically reviewed by an independent data monitoring committee, see separate charter.

Subjects will be requested to refrain from making any significant dietary changes throughout the duration of the study. Subjects should be reminded to maintain an adequate fluid intake during their scheduled visits.

Subjects completing the 4-week double-blind treatment period will be eligible to enroll and continue receiving study medication in Study 0170. The final study visit for those subjects who do not complete the 4-week double-blind treatment period or who choose not to continue into Study 0170 will be the follow-up visit (V7). This visit must be completed two weeks from the date of the last dose.

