## 26. Collect and review study medication

### 6.3.7. Follow-up Day 43 – Visit 7

The follow-up visit is applicable only for those subjects that will not proceed to Study 0170 and will be completed two weeks from the date of the last dose.

The following procedures will be performed on the Day 43 visit (+/- 3 days):

The following procedures are listed in the recommended order, however flexibility for scheduling is permitted:

1. Review concomitant medications and smoking usage

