### 8.6.2. Adverse Event Data

The AEs will be coded to the preferred terms (PTs) of the Medical Dictionary for Regulatory Activities (MedDRA®). Summaries will present by system organ class (SOC), preferred term, and severity (mild, moderate, severe), the number and percentage of subjects for whom events were reported.

In general, a treatment-emergent adverse event (TEAE) will be defined as any AE that begins on or after the date and time of the first dose of study medication and up to the date of last dose of study medication plus the number of days in the follow-up period.

The number and percentage of subjects who experience TEAEs will be summarized. Summaries of TEAEs will include the following:

- [REDACTED]
- [REDACTED]
- [REDACTED]
- [REDACTED]
- [REDACTED]
- [REDACTED]
- [REDACTED]
- [REDACTED]
- [REDACTED]

All AEs reported will be listed by subject. A listing will be provided for all subjects who experience an SAE. Listings will also be provided for subjects who discontinued study treatment prematurely because of AEs and subjects who temporarily interrupted study treatment because of AEs. The AESIs, as described in Section 7.1.4, will be listed and summarized.

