7.2. Subject Disposition and Completion Status

Subject disposition will be summarized for all randomized subjects by treatment group. The summary will include the counts and percentages of subjects in each analysis set as well as of subjects who:

- Were randomized and treated with study drug
- Were randomized and not treated with study drug
- Completed the 4-week treatment period
- Didn't complete the 4-week treatment period and the reason for not completing it (adverse event, loss of follow-up, noncompliance with study drug, physician decision, pregnancy, protocol violation, study terminated by Sponsor, and other)
- Completed the study
- Didn't complete the study and the reason (adverse event, loss of follow-up, noncompliance with study drug, physician decision, pregnancy, protocol violation, study terminated by Sponsor, and other)
- Continued to Study 0170
- Didn't continue to Study 0170 and the reason (did not complete study, chose not to continue, and other)

A listing of subject disposition will include the FAS status, the date of informed consent signed, the date of first dose and last dose of study drug, the primary reason for discontinuation of study treatment, the date of last visit, the study completion status, the primary reason for study termination, and the date of last contact.

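### Study 0169 TEAE percentages combine windows of about 28 and about 42 days, so the comparison between arms depends on completion and rollover

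*SAP*

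**What the plan says.** SAP 9.1 sets the general TEAE window from first dose "up to 14 days after the date of last dose of study drug". It then makes an exception for subjects who roll over: "any AE occurs after Study 0170 Visit 1 (Study 0169 Visit 6) will be considered as a TEAE for Study 0170", and such events "will not be included in the AE summary for Study 0169 to avoid double counting". The stated reason is thus that no event should be counted in both studies.

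The protocol (8.6.2) defines the window as running "up to the date of last dose of study medication plus the number of days in the follow-up period". Its readable text has no rollover exception.

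Who rolls over is described in protocol 3.1: "Subjects completing the 4-week double-blind treatment period will be eligible to enroll and continue receiving study medication in Study 0170". The last visit for subjects who do not complete treatment "or who choose not to continue into Study 0170 will be the follow-up visit (V7"). Protocol 6.3.7 agrees: "The follow-up visit is applicable only for those subjects that will not proceed to Study 0170". Subjects who do not roll over are therefore of two kinds: early terminators, and completers who decline.

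SAP 9.1 reports TEAEs as numbers and percentages of subjects by treatment group. The introduction to SAP section 9 says that safety data are in general not tested. SAP 7.2 tabulates by treatment group who continued and who did not, including "Didn't continue to Study 0170 and the reason (did not complete study, chose not to continue, and other").

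**The concern.** Among completers, the 14 days after the last dose count only for those who decline Study 0170. Whether a subject completes and then continues is settled after randomisation, and tolerability or benefit could plausibly affect both. If the mix of rollover, declining and early stopping differs by arm, the two TEAE percentages refer to different average observation periods. Part of any difference between them would then come from window length and not from risk.

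The same windows apply to the serious, severity, relatedness and special-interest summaries, and to the table of TEAEs above 3%. The exposure summary in SAP 9.2 measures dosing duration, not time at risk for a counted event, so it does not correct for this.

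Even with equal rollover in both arms, the percentages have no single time frame: they combine on-treatment events in everyone with post-treatment events in some.

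**Working it through.** **Inputs from the documents.** Visit 6 is nominally study day 28 (SAP Table 3), which is Day 29 in the protocol's numbering, with a window of ±3 days. The post-dose extension is 14 days (SAP 9.1). The documents give no TEAE rate and no rollover rate; those used below are assumptions.

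**Step 1: window per subject.**
- Completer who rolls over: study days 1 to 28, so about 28 days.
- Completer who declines: 28 + 14 = 42 days. This agrees with the follow-up visit on protocol Day 43, which is study day 42.
- Ratio: 42/28 = 1.50. Across the visit window it is 39/25 = 1.56 to 45/31 = 1.45.
- Early terminator with last dose on study day 7, 14 or 21: 7 + 14 = 21, 14 + 14 = 28, 21 + 14 = 35 days.

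**Step 2: gap made up of declining completers.** Assume equal true risk in both arms and a constant hazard that continues for 14 days off drug. Let p28 be the 28-day risk. Then p42 = 1 − (1 − p28)^1.5, and the spurious difference is the gap in the share of declining completers × (p42 − p28).

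| p28 | p42 | 10-point gap | 30-point gap |
|---|---|---|---|
| 5% | 7.4% | 0.2 points | 0.7 points |
| 20% | 28.5% | 0.8 points | 2.5 points |
| 40% | 53.5% | 1.4 points | 4.1 points |
| 60% | 74.7% | 1.5 points | 4.4 points |

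At p28 = 40%, declining shares of 10% and 30% give 0.90 × 40 + 0.10 × 53.5 = 41.4% and 0.70 × 40 + 0.30 × 53.5 = 44.1%, a difference of 2.7 points. Shares of 15% and 40% give 42.0% and 45.4%, a difference of 3.4 points. With equal shares the difference is 0.

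**Step 3: gap made up of early stops.** Keep p28 = 40% and non-rollover of 10% versus 30%. Let 10% decline in both arms, and let the extra 20% in the second arm stop early.
- Last dose on day 14 (28-day window, risk 40%): 41.4% versus 41.4%, difference 0.
- Last dose on day 7 (21-day window, risk 1 − 0.6^0.75 = 31.8%): 41.4% versus 0.70 × 40 + 0.10 × 53.5 + 0.20 × 31.8 = 39.7%, difference −1.6 points before rounding.

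The same rollover gap therefore gives +2.7, 0 or −1.6 points, depending on who makes it up.

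**Step 4: scale.** SAP 4.4 sets a minimum of 76 MSA subjects as 40% of enrolment, which implies 76/0.40 = 190 in total, or 95 per arm at 1:1. At a risk of 40% the standard error of a difference is √(2 × 0.4 × 0.6/95) = 7.1 points.

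**Step 5: effect of a common cut.** Cut everyone at the earlier of last dose + 14 days and Visit 6 (day 28). A completer who rolls over has 28 days and one who declines has min(42, 28) = 28. Stops on days 14 and 21 also have 28. A stop on day 7 still has 21. The difference among completers disappears; the shorter window for stops before day 14 remains.

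**The case against.** The cut at Visit 6 has a sound and stated reason. Rollover subjects go on taking study medication under another protocol, and their later events are counted there. The protocol's phrase about days in the follow-up period can be read as adding nothing for a subject who has no follow-up visit. Rollover and its reasons are tabulated by arm, adverse events are listed by subject, and safety is descriptive. All of this stands. It justifies where the rollover subjects are cut, but it does not supply a matching cut for the others.

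A reader might infer that the arm with fewer rollovers always gets more observation time and so a higher rate. The documents do not support that. Rollover requires completion, so an arm can have fewer rollovers because of early stops, and a stop before about day 14 leaves a window shorter than 28 days. Step 3 shows the sign reversing.

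A reader might also take 2.7 to 3.4 points as the expected size. Those figures need a gap of 20 to 25 points made up entirely of declining completers, for which the documents give no basis. They are also under half a standard error at about 95 per arm. A constant hazard may overstate drug-related events after dosing stops.

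Finally, the list of TEAE summaries in protocol 8.6.2, SAP 9.1.1 and SAP Appendix 1 are redacted. An on-treatment or exposure-adjusted table could be there, so the point covers the readable text only.

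**Conclusion.** The point holds as a minor one. Under SAP 9.1, crude TEAE percentages by arm depend on completion and rollover status, because completers are counted for about 28 or about 42 days according to whether they enter Study 0170. If rollover differs by arm, the comparison mixes windows of different length.

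Neither direction nor size can be fixed from the documents. Assuming equal true risk, a constant hazard and 28-day risks of 5% to 60%, a 10-point gap in declining completers produces about 0.2 to 1.5 percentage points. A gap that comes from early stops can produce nothing or the opposite sign. Equal rollover with equal risk produces no spurious difference. The documents do not support saying that the rule will hide or create a safety difference, only that the planned tables cannot separate window length from risk.

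**What to change.** Keep the TEAE definition in SAP 9.1 and its tables. Add a TEAE summary by arm that cuts every subject at the earlier of last dose + 14 days and Visit 6, using nominal study day 28 where there is no Visit 6. The schedule gives Visit 6 and the early termination visit one shared column, so state that an early termination visit does not count as Visit 6 for this cut. Tabulate later follow-up events in subjects who do not roll over separately, and name the common-cut table as the one for comparing arms.

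Replacing the main tables with a first-dose-to-last-dose window would be a worse choice: it would drop post-dose events in subjects who stopped because of an adverse event, and early terminators would still have shorter windows.

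The change needs no new data and still counts no event in both studies. It costs a short addition to SAP 9.1 and one extra set of tables. It does not lengthen the window for stops before day 14, which a table footnote should say.
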